## 1.0 Research Design

### 1.1 Purpose/Specific Aims

The purpose of this proposed pilot study is to test different recruitment approaches, examine the acceptability and feasibility of 3h sleep extension in 14-17 year olds, and determine if there are any issues with having adolescents wear the two devices we use to measure sleep and physical activity.

#### A. Objectives

The proposed study will serve as a pilot for a planned future study. In the future study, adolescents will be asked to increase time-in-bed (TIB) for sleep by ~3h/night in order to assess how sleep extension impacts markers of insulin sensitivity.

#### B. Research Question(s)

Aim 1: Determine the additional amount of sleep short-sleeping-adolescents (~7h TIB/night) will obtain when asked to increase time-in-bed to 10h/night for seven consecutive nights compared to those who are not asked to increase time-in-bed.

Aim 2: Determine if adolescents are able to comply with study demands: wearing two devices (one on wrist and one on hip) and completing daily sleep diaries and call-ins for seven days.

Aim 3: Acquire participant feedback regarding feasibility and acceptability of increasing TIB for sleep to 10h/night using a questionnaire and semi-structured interview.

### 1.2 Research Significance

Short sleep has become a significant health concern in adolescents; approximately 73% of adolescents in the U.S. self-report sleeping less than the recommended 8-10 h/night (1), and many exhibit irregular sleep patterns with short sleep during school nights and longer sleep on weekends (2). Observational studies reliably demonstrate a relationship between adolescent short sleep and adverse health outcomes (3-5). Therefore sleep interventions that successfully increase sleep duration are needed in this age group. Furthermore, adolescence may represent an important stage in the lifespan to target a sleep intervention as it is a developmental period during which lifestyle patterns – such as sleep, eating, and activity behaviors – are established and endure into adulthood(6). It is critical to first assess the feasibility and acceptability of increasing sleep duration in short sleeping adolescents prior to conducting a larger experimental study which will examine the impact of increased sleep on metabolic health outcomes.

### 1.3 Research Design and Methods

Adolescents (14-17y) will be recruited to participate in an observational pilot study. Participants will be asked to wear a sleep monitor on the wrist, a physical activity monitor on the hip, and complete a brief daily sleep diary and call-in procedure for 1 week. Approximately 15 subjects will be assigned to increase their time-in-bed for sleep by ~3h per night and 15 subjects will maintain their normal sleep schedule. The proposed study will incorporate a mixed-methods approach to gather information about the feasibility of implementing a similar sleep protocol in a future study.

**A. Screening Interview:** Participants will undergo a phone screen which will be carried out by the trained study coordinator or a research assistant. During the phone screen, participants will be asked to provide oral consent so information can be recorded to determine participant eligibility. If participants are determined to be eligible, they will be invited by the study staff to the sleep center for an orientation to the study. Prior to scheduling families, research staff will ensure that there are no planned family vacations, changes in typical family routine that might impact sleep (e.g., planned sleepovers), or current minor illness(e.g., colds) that might disrupt sleep or result in the child needing to take medications that might impact sleep. The study will be timed around family's schedules to maximize adherence to study protocol. Subjects who expressed interest to participate in future research studies will be screened again to determine eligibility following modification Mod2018002469 to the study protocol. Only subjects who gave permission to be contacted again will be screened again.

**Orientation:** When the family arrives to the sleep center, study staff will first collect additional eligibility information (height and weight measurement, additional information about the adolescent's typical sleep, availability to complete study

schedule). Note: if the subject is not eligible based on BMI, the height and weight data will be destroyed immediately. If the adolescent is eligible, study staff will provide an overview of the study and will review the Informed Consent/Accent forms with the family.

Participants will be asked to provide written informed consent/assent prior to data collection. After participants agree to participate and are enrolled in the study, participants will complete the following questionnaires: 1) Children's Chronotype Questionnaire (7), 2) Demographic Questionnaire, 3) Sleep Disorders Inventory for Students- Adolescents (SDIS-A) (8) 4) Mood Questionnaire (9), the Perceived Stress Scale (10) and the Freiburg Mindfulness Inventory (11) (NOTE: questionnaires will be converted to an online format using Qualtrics, an online survey platform). Participants will also complete a battery of cognitive tests during the orientation to assess how sleep affects cognitive function (12). A final check for eligibility (based on the sleep disorder questionnaire) will be conducted. Adolescents who remain eligible will be provided with wrist actigraphs, waist accelerometers and sleep diaries and instructed on their use for the next 7 days. To assist in scoring the actigraphs, participants will be asked to call a time-stamped voice mail (or text) twice daily: before bedtime and when they wake up. Research staff will follow up with families who do not call in or text.

A consistent wake time will be established with families randomized to the 10 h time-in-bed condition based on the adolescents' typical schedules. Bedtime will then be calculated as 10 h prior to wake time. Families will be provided with handouts (See Tasks Overview for Families) that explicitly state the participant's bedtime and wake time for each day during the sleep schedule to ensure adherence to the protocol. Research staff will also discuss the participant's bedtime routine and will ask that participants begin that routine with the sufficient time so that it can be completed prior to the prescribed bedtime. Research staff will reiterate that the participant must be lying in bed with the lights out at the prescribed bedtime, and that an alarm clock should be set for the prescribed wake time. Parents will also be asked to ensure that the adolescent goes to bed and wakes up (and gets out of bed) on time. Participants will be instructed to remain in bed with the lights off even if they have difficulty falling asleep or wake up earlier than the prescribed wake time. Participants must refrain from engaging in any activity (e.g., reading a book or engaging in social media) during the prescribed TIB.

Handouts (See Sleep Health Education Information Sheet) on sleep hygiene practices (i.e., strategies to ensure a good night's sleep) will be reviewed and provided to families. These include a list of caffeinated foods/beverages to avoid after 2pm, not watching TV, using computer/smartphone/tablet or play video games as part of the bedtime routine, and ensuring that the adolescent has a quiet, cool, and dark sleep environment. Research staff will discuss potential barriers to following the protocol and provide strategies to overcome these barriers (e.g., providing participants with an eye mask to block out excess light, discussing the use of fans or white noise machines to decrease noise, turning phone/tablets off or giving these devices to parents when it is time for bed and recording TV shows that begin late at night).

Subjects who are randomized to the control condition will be asked to maintain their typical bedtime and wake times. These subjects will be instructed to wear wrist actigraphs, waist accelerometers, complete sleep diaries and call-ins for 7 days. Handouts and resources on sleep hygiene practices will be reviewed at the end of the study.

Study staff will conclude the orientation session by answering any remaining questions that the family has and scheduling the follow-up visit.

**Week-long study protocol:** Participants are instructed to wear the sleep monitor (on wrist) 24h a day for the entire 7 day period and to wear the physical activity monitor (on hip) during all waking hours for the entire 7 day period. Participants will be given a 7-day sleep diary to complete daily. This provides an additional monitor of sleep which assists in analysis of wrist actigraph data and serves as an effective behavioral strategy to increase adherence to the protocol via self-monitoring. Participants will also be asked to call in twice daily (just prior to bedtime and upon waking in the morning) to a time-stamped voice mail box or send a text to the study's Google voice account. If a family fails to call in/text or calls in bed bed/wake times are outside prescribed times, research staff will follow-up with families by phone to ensure protocol adherence. Research staff will also maintain a rolling calculation of adherence to the sleep schedule for subjects asked to complete 10h TIB.

**Follow-Up Visit:** The participant and his/her parent will return to the sleep center approximately 1 week after the orientation to return the wrist actigraph, waist accelerometer and sleep diary. Study staff will administer an accelerometer question form and an actigraph question form to inquire about any discrepancies in recorded diary entries, actigraphy data and call-in log information. This will take place in the form of a semi-structured interview. Additionally, participants will be asked to repeat the mood questionnaires, Perceived Stress Scale and the Freiburg Mindfulness Inventory (11)complete an exit-survey (Acceptability/Feasibility Questionnaire) and semi-structured interview related to their overall impressions of the study to gain more information about study feasibility. The cognitive battery will be administered again for assessment of cognitive function after prescribed bed-time (12)/control condition. Participants will be provided \$10 for each 24-hour period that they follow study procedures. Specifically, each night that they call/text prior to getting into bed, get into bed at their prescribed bedtime (i.e., the actigraph is consistent with the reported bedtime), call/text in the morning right when they wake and get out of bed at the prescribed wake time (i.e. the actigraph is consistent with the reported wake time), the participant will earn \$10 (total possible: \$70). Our research team has found that this strategy results in very high adherence to experimental sleep protocols.

**B.** Participants will be asked to participate in a phone-screening interview (15-20 minutes). If initially determined eligible by the phone screen, participants will be invited to visit the sleep center for a study orientation (1.5-2 hours). During the orientation, informed consent will be obtained (10-20 minutes). Participants will be asked to wear a wrist actigraph and waist accelerometer for the week following orientation (1 week). Participants will be expected to wear devices during the entire week as well as call a time-stamped voicemail during wake and bed times and complete sleep diaries daily. Participants will be asked to report to the study center approximately one week after the orientation date for a follow-up visit (1-1.5 hours) to deliver devices, undergo a semi-structured interview about the sleep data that was collected, and provide study staff with feedback regarding the study.

#### **1.4 Preliminary Data**

N/A: Adherence to changes in sleep duration as prescribed in a sleep protocol has not been studied in adolescents.

#### **1.5 Sample Size Justification**

The proposed study's purpose is to serve as a pilot study to gain exploratory data on approximately 30 adolescents to explore sleep health study feasibility in New Brunswick, New Jersey. Therefore, power analysis was not performed.

#### **1.6 Study Variables**

##### **A. Independent Variables, Interventions, or Predictor Variables**

The proposed study is a pilot to assess the feasibility of increasing adolescent time-in-bed for sleep to 10 h/night for seven consecutive nights. Individuals who regularly sleep 7h/night will be recruited to participate in the research study. A sleep protocol will be implemented to either increase individual sleep by ~3 h/night or maintain a typical sleep schedule. Study staff will work with the participants to determine a bedtime wake time schedule that will increase number of hours from 7h/night to 10h/night. The purpose of this research is to gain new information about sleep study feasibility.

##### **B. Dependent Variables or Outcome Measures**

**Sleep:** Sleep will be monitored using the Actiwatch Spectrum Plus (Phillips Respironics, Murrysville, PA). Wrist actigraphy is a widely used, reliable and valid approach for measuring sleep (13-15). The device is worn on the non-dominant wrist across the 24-hour period and monitors motor activity to obtain continuous recordings of sleep-wake states. In this study, the device will be configured to store data in a 1-minute epoch in accordance with pediatric reliability and validity studies (13, 16). Epochs are scored as sleep or wake by Actiware 6.0 software using an algorithm that modifies activity counts during a single epoch by activity produced in the surrounding two minute time period (16). **The primary variable of interest is the actigraph**

**measured sleep period, which is the period between actigraph-estimated sleep onset and wake.** Participants will be asked to press a button on the device when they go to bed and once when they wake up. Additionally, daily call-ins will provide an additional measure of bedtime and waketime and daily sleep diaries will be used to collect participants' estimate of bedtime and wake time, awakenings during the night, and daytime sleep (i.e. naps). This information is critical for verifying and scoring actigraphy data and provides an additional measure of sleep duration.

**Physical activity:** Physical activity will be tracked using the Actigraph GT3X (ActiGraph Corp, Pensacola, FL). Hip-worn accelerometry is a reliable and valid objective assessment of physical activity in adolescents (17, 18). Participants will be instructed on how to wear the device (device placement, only to wear during waking hours, whether the device can be worn in water etc.). Standard procedures for scoring (i.e. number of valid days, minimum amount of daily wear time needed and detection of non-wear time) and an established algorithm for determining the amount of time spent in moderate/vigorous activity will be used (17). **For this pilot study, the primary variable of interest is daily wear time.**

**Acceptability/Feasibility:** The acceptability and feasibility of increasing time in bed for sleep to 10h/night will be assessed with a questionnaire and a semi-structured interview to follow up on participant questionnaire responses. Of interest will be the participant's perceptions of **1) how challenging obtaining more sleep is during school nights is, 2) benefits they experienced as a result of sufficient sleep; and 3) what type of messaging and strategies should be used in a future sleep intervention.** These responses will guide future studies examining the effect of sleep extension on metabolic health and aid in the development of sleep intervention in adolescents. The research team has successfully used this multi-method approach in previous studies. Research staff will also maintain a rolling calculation of adherence to time-in-bed with sufficient adherence defined as ≥85% of the prescribed time-in-bed.

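### Daily wear time in hours, the primary hip-monitor variable, tracks Aim 2 compliance imperfectly because assignment changes the hours available for wear

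*Protocol*

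**What the plan says.** Section 1.1, part B, Aim 2 asks whether adolescents can comply with the study demands, including wearing a wrist device and a hip device. For the hip monitor, section 1.6, part B names one variable: "For this pilot study, the primary variable of interest is daily wear time". No denominator is attached.

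The same paragraph tells participants "only to wear during waking hours", and section 1.3 instructs them "to wear the physical activity monitor (on hip) during all waking hours for the entire 7 day period".

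The two conditions set different days. In the extension condition (section 1.3), "Bedtime will then be calculated as 10 h prior to wake time". For the comparison group, "Subjects who are randomized to the control condition will be asked to maintain their typical bedtime and wake times". Aim 1 describes the population and the request together: "short-sleeping-adolescents (~7h TIB/night) will obtain when asked to increase time-in-bed to 10h/night".

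Three further statements bear on the point:

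- Section 1.6, part B counts sleep adherence as sufficient from 85% of the prescribed time in bed.
- Section 6.1, part A plans mainly descriptive statistics for sleep and physical activity.
- Section 1.8, part A has staff review when the hip device was off and why.

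**The concern.** A compliance measure should give the same value to two participants who follow the instruction equally well. Hours of hip wear do not, because the instruction covers the waking day and the intervention shortens that day. A control and an extension participant who both wear the monitor whenever they are up record different hours.

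Within the extension arm the two kinds of adherence pull against each other. A participant who ignores the longer schedule has more hours in which to wear the monitor than one who keeps to it.

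At stake is how Aim 2 is read. The pilot exists to inform a larger study, with 15 participants per arm and no power analysis, so its descriptive summaries are its main product. Lower hours in the extension arm could be taken as poorer tolerance of the device when they reflect only a longer time in bed.

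**Working it through.** The protocol gives no target or expected value for wear time, so there is no stated figure to reproduce.

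**Inputs from the protocol.** Extension time in bed 10 h (section 1.3). Habitual time in bed about 7 h (section 1.1, Aim 1), which controls are asked to keep. Adherence floor 85% (section 1.6, part B).

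**Formula.** Attainable wear = 24 h − time in bed. Relative gap = (control − extension) / control.

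**Main figures.**
- Control: 24 − 7 = 17 h.
- Extension, full adherence: 24 − 10 = 14 h. Gap 3 h; 3/17 = 17.6%.
- Extension at the floor: 0.85 × 10 = 8.5 h in bed; 24 − 8.5 = 15.5 h. Gap 1.5 h; 1.5/17 = 8.8%.
- Extension participant who stays at 7 h in bed: 17 h, which is 3 h more than a fully adherent one.

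**Same hours, different compliance.** 12 h worn is 12/14 = 85.7% at 10 h in bed, 12/15.5 = 77.4% at the floor and 12/17 = 70.6% in control.

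**Sensitivity to control time in bed (assumed values).** Section 4.2 sets about 7 h of sleep on school nights only, and section 1.2 notes longer weekend sleep, so controls may average more than 7 h in bed.

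| Control time in bed | Control window | Gap to 14 h | Gap to 15.5 h |
|---|---|---|---|
| 7 h | 17 h | 3.0 h (17.6%) | 1.5 h (8.8%) |
| 7 h, with two nights at 8 h | 16.71 h | 2.71 h (16.2%) | 1.21 h (7.3%) |
| 7 h, with two nights at 9 h | 16.43 h | 2.43 h (14.8%) | 0.93 h (5.7%) |
| 7 h, with two nights at 10 h | 16.14 h | 2.14 h (13.3%) | 0.64 h (4.0%) |
| 7.5 h | 16.5 h | 2.5 h (15.2%) | 1.0 h (6.1%) |
| 8 h | 16 h | 2.0 h (12.5%) | 0.5 h (3.1%) |
| 8.5 h | 15.5 h | 1.5 h (9.7%) | 0 |

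**Sensitivity to literal waking hours.** Assume sleep is 85%, 90% or 95% of time in bed. Waking hours at 10 h in bed are then 15.5, 15.0 and 14.5 h.
- Controls with 7 h in bed: 18.05, 17.70 and 17.35 h awake. Gap 2.55, 2.70 and 2.85 h (14.1%, 15.3%, 16.4%).
- Controls with 7 h asleep: 17 h awake. Gap 1.5, 2.0 and 2.5 h (8.8%, 11.8%, 14.7%).
- Extension at the floor, against controls with 7 h asleep: 16.775, 16.35 and 15.925 h awake. Gap 0.23, 0.65 and 1.08 h (1.3%, 3.8%, 6.3%).

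**Check of the remedy.** Dividing by the window gives 17/17, 15.5/15.5 and 14/14, all 100%, so equal compliance gives equal values. If naps stayed in the window, an assumed 1 h nap without the device would count as 1/17 = 5.9% or 1/14 = 7.1% non-wear although the instruction was followed.

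**The case against.** The strongest reply is that the protocol never says absolute hours. It says daily wear time, and how that is summarised could be settled in an analysis plan not seen here. It is true that the text does not rule out a percentage. But the protocol itself chooses and names the primary hip variable, and as named it carries no denominator. The same section does express sleep adherence as a percentage of what was prescribed.

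Second, Aim 2 is not framed as a comparison between arms; only Aim 1 is. That limits the consequence but does not remove it: pooled hours mix two windows, and within the extension arm hours still fall as sleep adherence improves.

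Third, the protocol already applies scoring rules for valid days, minimum wear and non-wear, and reviews off-periods with the participant. These are useful and are not challenged here. As listed, they do not adjust for a waking day that differs by condition, and the review gives reasons rather than a compliance measure.

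Fourth, a percentage needs bed and wake times from sources whose completion Aim 2 is itself testing. Those times are likeliest to be missing in the least compliant participants. This objection stands, and the fix has to deal with it.

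A reader might also infer that the planned mixed-model ANOVAs would show a spurious arm difference in wear time. The documents do not support that. Section 6.1 names changes in sleep and physical activity, states no test of wear time, and gives no standard deviation from which a false-positive probability could be worked out.

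**Conclusion.** The point holds as a minor one. Read as compliance, hours of wear understate the extension arm relative to control. The gap is at most 3 h/day (17.6%), which needs 10 h against 7 h in bed on every night. It is 1.5 h/day (8.8%) at the 85% floor with 7 h controls. With the longer control times in bed assumed above (two longer weekend nights, or an average of 7.5 to 8 h), it is about 2.0 to 2.7 h at full adherence and about 0.5 to 1.2 h at the floor. It vanishes if controls average 8.5 h and the extension arm sits at the floor. Using time in bed to stand for time without the monitor is an assumption; the literal waking-hours figures are smaller but point the same way.

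The effect is confined to the descriptive reading of Aim 2. It would be too strong to say that raw hours are invalid, that participants will be misclassified as non-compliant, or that Aim 2 fails. Hours remain a correct description of time worn, no hours threshold for compliance is stated, and Aim 2 also rests on the wrist device, diaries and call-ins.

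**What to change.** Keep daily wear hours. For Aim 2 compliance, add the percentage of the expected wear window during which the hip monitor was worn, reported by arm and overall. Define the window as 24 h minus the recorded bed-to-rise period and minus diary-recorded naps. The inputs are already collected: section 1.6, part B states "Participants will be asked to press a button on the device when they go to bed and once when they wake up", and the diary and call-ins supply the rest.

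State the handling of missing times. Where one source of bed or wake time is missing, use the next available of actigraph, diary and call-in. Report the number of days on which the window cannot be determined, and show raw hours for those days, so that the least compliant participants are not dropped.

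The cost is a few sentences and one derived variable, with no new data and no change in conduct. The downside is that the percentage depends on the completeness and scoring of bed, wake and nap times. It also leaves out time awake in bed. That departs from the literal waking-hours instruction and may differ by arm, since extension participants are told to stay in bed even when they cannot sleep. Showing raw hours beside the percentage lets the reader judge both.
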